| Statistical Methods: | 
Analysis will include the following populations:
 
• CITT Population (clinical intent-to-treat): includes all randomized subjects.• Safety Population includes all randomized subjects who received at least one dose of the study treatment.• MITT Population (mycological intent-to-treat): includes all randomized subjects who had a positive baseline fungal culture.• MPP Population (mycological per protocol): includes all randomized subjects who had a positive baseline fungal culture, were compliant with the assigned study treatment, and completed the evaluation at the test-of-cure (evaluation phase) within the designated visit window and have no major protocol violations. 
All efficacy analyses performed on the MITT population will be repeated on the MPP population.
 
Sample size calculation:
 
Clotrimazole otic solution should be statistically superior to the placebo ($p<0.05$) with regard to the therapeutic cure at the test-of-cure visit, using the MITT population.
 
Assuming a significance level of 5% and a desired statistical power of 95%, a placebo effect of 30%, and a 2:1 allocation schedule, the total number of patients needed to detect a difference of 30% in the therapeutic cure (100% relative increase) is 150 (100 with clotrimazole and 50 with placebo). The suspected dropout rate due to negative mycological culture at baseline is 21% that leads to a required inclusion of 191 patients (127 for the clotrimazole group and 64 patients for the placebo group).
 
As this is a twin trial if the CLEAR-1 study is completed before this study (CLEAR-2) an updated sample size computation will be performed for CLEAR-2 utilizing the results from the CLEAR-1 given the results from the CLEAR-1 will provide a more accurate estimation of the cure rate for treatment and control arms.”
 |
|-----------------------------|---|

TABLE OF CONTENTS

| | |
|---|-----------|
| 1. INVESTIGATORS AND STUDY ADMINISTRATIVE STRUCTURE | 16 |
| 2. INTRODUCTION..... | 17 |
| 2.1 Background..... | 17 |
| 2.2 Rationale for the Study | 19 |
| 2.3 Risk-Benefit Assessment..... | 19 |
| 3. OBJECTIVES | 21 |
| 3.1 Primary Objective | 21 |
| 3.2 Secondary Objectives..... | 21 |
| 4. OVERALL DESIGN AND PLAN OF THE STUDY..... | 22 |
| 4.1 Overview | 22 |
| 4.2 Justification for Study Design | 25 |
| 5. STUDY POPULATION..... | 26 |
| 5.1 Inclusion Criteria | 26 |
| 5.2 Exclusion Criteria | 26 |

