10.1.4 Analysis Populations

There will be 4 populations defined for this study: Safety, Clinical intent-to-treat (CITT), Mycological intent-to-treat (MITT), and Mycological per-protocol (MPP).

The **Safety population** will include all patients who received any study medication.

The **CITT population** will include all patients who were randomized.

The **MITT population** will include all CITT patients who had a positive baseline fungal culture for *Aspergillus spp* and/or *Candida spp*.

The **MPP population** will include all randomized patient who had positive baseline culture for *Aspergillus spp* and/or *Candida spp* and who:

- Satisfied all inclusion and exclusion criteria;
- Did not receive any prohibited concomitant medications (except if it is considered rescue medication);
- Did not have any other major protocol violations;
- Completed Visit 2, Visit 3 and Visit 4 (unless the subject was deemed a clinical failure at an earlier visit than Visit 4) with the designated visit window
- Had compliance rates between 80% and 100% as defined in Section 10.1.8 (patients who are deemed Clinical Failures are to be included if they had compliance rates between 80% and 100% during the first 3 days of study treatment).
- Had mycological results (when subject has material to culture) from Visit 1, Visit 2, Visit 3 and/or Visit 4 unless the subject was deemed a clinical failure at an earlier visit than Visit 4.

For the CITT and MITT populations, the treatment group of a patient will be determined by the treatment group to which the patient was randomized.

For the Safety and MPP populations, the treatment group of a patient will be determined by the treatment the patient received, not necessarily the group to which he or she was randomized. The Safety population will be used for all safety analyses.

The primary populations for efficacy analyses will be the MITT population.

The populations to be used for each of the secondary efficacy endpoints will be detailed in the Statistical Analysis Plan.

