### 3.2.4 Mycological per-protocol (MPP)

The MPP population will include all randomized patient who had positive baseline culture for *Aspergillus spp* and/or *Candida spp* and who:

- Satisfied all inclusion and exclusion criteria;
- Did not receive any prohibited concomitant medications (except if it is considered rescue medication);
- Did not have any other major protocol violations;
- Completed Visit 2;
- Completed Visit 3 and Visit 4 (unless the subject was deemed a clinical failure at an earlier visit than Visit 4);
- Completed Visit 4 within the designated visit window;

- Had compliance rates between 80% and 100% as defined in Section 3.3.7 (patients who are deemed Clinical Failures are to be included if they had compliance rates between 80% and 100% during the first 3 days of study treatment);
- Had mycological results (when subject has material to culture) from Visit 1, Visit 2, Visit 3 and/or Visit 4 unless the subject was deemed a clinical failure at an earlier visit than Visit 4.

For the CITT and MITT populations, the treatment group of a patient will be determined by the treatment group to which the patient was randomized.

For the Safety and MPP populations, the treatment group of a patient will be determined by the treatment the patient received, not necessarily the group to which he or she was randomized. The Safety population will be used for all safety analyses.

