#### *3.3.2 Protocol Deviations*

Protocol deviations are defined as violations from the procedures outlined in the protocol. Major protocol deviations are protocol violations likely to affect the study results and leading to the exclusion of the subject from the MPP.

Once the database has been completed and considered as “clean”, a data blind review will be conducted before the database lock in order to identify all major protocol violations and assign subjects into each of the analysis sets as defined in Section 3.2.

Patients with protocol deviations will be presented in the data listings. Counts and percentages of subjects with protocol deviations by deviation category will be summarized by treatment and in total based on CITT population.

The protocol deviations are considered critical (or very serious) and major (or serious), according to the following definitions:

- Critical or very serious: Deviations affecting / they have adversely affected the rights, safety or welfare of subjects and / or the quality and integrity of data
- Major or serious: Deviations that may affect / have adversely affected the rights, safety or welfare of subjects and / or the quality and integrity of data.

In addition, the protocol deviations related to COVID-19 will be categorized and summarized by treatment and in total based on CITT population separately.

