## 5 CHANGES FROM PROTOCOL-SPECIFIED STATISTICAL ANALYSES

The following items were changed between the protocol and the SAP:

- The secondary endpoint of Mycological cure was modified to “Mycological cure at Visits 2, 3 and 4.”.
- Definition of mycological response when baseline culture was positive was modified. Protocol states “Presumed persistence if there is no material to culture and the Overall Clinical Outcome is not Clinical Cure”. This definition was updated to “Presumed Persistence if there is no material to culture or sample was not taken or sample was not shipped to lab and the Overall Clinical Outcome is not Clinical Cure” in SAP. In protocol, Reinfection was defined as “Reinfection if there is isolation of a new fungal pathogen different from the one eradicated or presumably eradicated” and was modified as “Reinfection if there is isolation of a new fungal pathogen different from the one present at Visit 1 and the initial pathogen is not present” in SAP. Reinfection was also added to the classification of mycological outcome at Visit 2. Superinfection was re-defined as “Superinfection if a new fungal pathogen not present at Visit 1 is isolated while the initial pathogen is also present (presence of a nonpathogenic organism will not be considered Superinfection)” for all visits in SAP.
- The protocol states that one of the inclusion criteria of MPP population is subject who “Completed Visit 2, Visit 3 and Visit 4 (unless the subject was deemed a clinical failure at an earlier visit than Visit 4) with the designated visit window”. This was modified as subjects who “Completed Visit 3 and Visit 4 (unless the subject was deemed a clinical failure at an earlier visit than Visit 4)” and “Completed Visit 4 within the designated visit window” in SAP. Visit 2 and Visit 3 out of window were removed from MPP exclusion criteria. Visit 2 not completed was added into MPP exclusion criteria.

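### SAP 3.2.4: the Visit 4 window criterion has no exemption, so as written it drops earlier clinical failures with no Visit 4 from the supportive per-protocol set

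*SAP*

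**What the plan says.** SAP 3.2.4 lists the MPP criteria under a lead-in that makes them cumulative. Two adjacent bullets matter here:

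- Completion: "Completed Visit 3 and Visit 4 (unless the subject was deemed a clinical failure at an earlier visit than Visit 4".
- Window: "Completed Visit 4 within the designated visit window", with nothing further.

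Three other clauses in the same list make room for patients who failed early. Rescue treatment does not count as a prohibited medication: "Did not receive any prohibited concomitant medications (except if it is considered rescue medication". Compliance for clinical failures is judged on the first 3 days only. The requirement for mycological results is waived for those who failed before Visit 4.

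Protocol 10.1.4 has a single criterion that holds both the exemption and the window: "unless the subject was deemed a clinical failure at an earlier visit than Visit 4) with the designated visit window". The protocol synopsis gives a shorter definition with no exemption: "completed the evaluation at the test-of-cure (evaluation phase) within the designated visit window and have no major protocol violations".

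SAP Section 5 lists the changes from the protocol. It repeats both new bullets and explains them in two sentences: "Visit 2 and Visit 3 out of window were removed from MPP exclusion criteria" and "Visit 2 not completed was added into MPP exclusion criteria". It does not mention withdrawing the failure exemption at Visit 4.

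**The concern.** A patient deemed a clinical failure at Visit 2 or 3 who then has no Visit 4 is let in by the completion bullet and shut out by the window bullet. Because every bullet must be met, the exemption from Visit 4 has no effect.

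Such patients are foreseeable. Under SAP 2.2.1, rescue medication prescribed at Visit 2 or Visit 3 means withdrawal from the study, and SAP 2.3.1.1.5 classes anyone who takes rescue medication as a clinical failure.

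As written, then, the rule removes patients because they failed, which is selection on outcome. It raises the MPP cure rate in any arm that loses such patients. The effect on the treatment difference depends on how many leave each arm. SAP 3.4.1 and 3.4.2 repeat the primary and secondary analyses on the MPP, and SAP Section 1 applies the same plan to both CLEAR-1 and CLEAR-2, so the wording carries through all of these.

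**Working it through.** **Step 1: apply the two bullets to each kind of patient.**

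| Patient | Completion bullet | Window bullet | In MPP on these two? |
|---|---|---|---|
| Not an earlier failure, Visit 4 in window | met | met | yes |
| Earlier failure who continues, Visit 4 in window | met | met | yes |
| Rescued patient who still attends Visit 4 in window (foreseen in Protocol 8.2.4) | met by exemption | met | yes |
| Earlier failure, no Visit 4 | met by exemption | not met | no |

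Only the last row is affected.

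**Step 2: was the loss intended?** The protocol's single bullet was split in two in the SAP, and the exemption stayed with only one half. Section 5 openly declares a stricter rule for Visit 2 and looser windows for Visits 2 and 3, but nothing about earlier failures at Visit 4. The three other clauses that keep these patients also point to a drafting slip. The synopsis wording points the other way, so the protocol itself has two versions.

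**Step 3: illustrate the size.** The plan gives no MPP figure to reproduce. Its design figures supply the inputs (SAP 2.2.4): 100 v 50 evaluable patients, 30% cured on placebo and a 30-point difference, so 60% on clotrimazole. As a check on those inputs, the pooled normal approximation gives 94.6% power at a two-sided 5% level, against the stated 95%.

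Assumptions: all 100 v 50 are otherwise MPP-eligible, and 60 v 15 are cured, leaving 40 v 35 failures. The number of failures with no Visit 4 is not in the documents and is varied.

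With r failures removed from an arm of n patients, the MPP cure rate is p = cured/(n − r). The 95% CI for the difference is d ± 1.96 × √[p₁(1 − p₁)/(n₁ − r₁) + p₀(1 − p₀)/(n₀ − r₀)].

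For example, removing 5 v 10 gives 60/95 − 15/40 = 0.632 − 0.375 = 0.257.

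| Failures removed (clotrimazole v placebo) | Cure rates | Difference, points (95% CI) |
|---|---|---|
| none | 60.0% v 30.0% | 30.0 (14.1 to 45.9) |
| 8 v 7 (20% of each arm's failures) | 65.2% v 34.9% | 30.3 (13.1 to 47.6) |
| 16 v 14 (40%) | 71.4% v 41.7% | 29.8 (11.0 to 48.5) |
| 24 v 21 (60%) | 78.9% v 51.7% | 27.2 (6.9 to 47.6) |
| 5 v 10 | 63.2% v 37.5% | 25.7 (7.8 to 43.5) |
| 10 v 5 | 66.7% v 33.3% | 33.3 (16.5 to 50.2) |

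For an equal share f, the difference is 0.6/(1 − 0.4f) − 0.3/(1 − 0.7f). Setting this to 0.3 and clearing fractions gives 0.084f² = 0.03f, so f = 0 or f = 0.03/0.084 = 0.357. The difference is slightly above 30 points up to a share of 35.7% and falls after that.

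A more uneven split moves it further. With 10% of clotrimazole and 50% of placebo failures removed (4 v an expected 17.5), it is 60/96 − 15/32.5 = 62.5% − 46.2% = 16.3 points.

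**Step 4: vary the eligibility assumption.** If only 80% of each arm is otherwise MPP-eligible (80 v 40, with 48 v 12 cured), the starting difference is 30.0 (12.2 to 47.8). Removing 4 v 8 gives 48/76 − 12/32 = 25.7 (5.7 to 45.6). Removing 8 v 4 gives 48/72 − 12/36 = 33.3 (14.5 to 52.2).

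**The case against.** The strongest reply is that Section 5 separates two reasons for exclusion, a visit not completed and a visit out of window. On that scheme the window bullet concerns only visits that took place, and a visit that never happened cannot be out of window. This is a sensible reading and probably the intended one. The bullet does not say it, though: it requires Visit 4 to be completed. The proposed rewording makes that reading explicit.

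A second reply is that the blinded data review before lock will apply the bullets sensibly, and that reasons for exclusion are summarised and listed (SAP 3.3.1). The listing would make any loss visible. But SAP 3.3.2 has the review "assign subjects into each of the analysis sets as defined in Section 3.2", which is the text in conflict, so the review has no other rule to fall back on.

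A third reply is that little is at stake. Much of this stands. The MPP is supportive, equal removal barely moves the difference, and no interval tabulated above reaches zero. If more placebo failures leave, the difference shrinks, which works against the test product. Nothing in the documents suggests the opposite pattern.

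Finally, a window that binds only attended visits still excludes an earlier failure who attends Visit 4 late. That is defensible for a patient who continues in the study, because that Visit 4 result is used in the analysis, but it is a choice and should be stated.

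**Conclusion.** The criterion is wrong as written. Taken literally, SAP 3.2.4 removes from the MPP the earlier clinical failures who have no Visit 4, whom the preceding bullet and three other clauses set out to keep, and Section 5 does not declare this.

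In the illustration the MPP difference runs from 25.7 to 33.3 points when 15 failures leave unevenly (5 v 10 or 10 v 5). It stays within 0.3 points of 30.0 in the equal-share cases of 20% and 40%. These figures rest on the design cure rates and on assumed removal counts. The contradiction in the text does not depend on them. The primary MITT analysis, its significance level and the sample size are not affected, so this should be corrected before lock but does not threaten the main conclusion.

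**What to change.** Before database lock, make the window bullet in SAP 3.2.4 conditional, for example: *where Visit 4 took place, its date fell inside the protocol window*. The completion bullet still requires Visit 4 of everyone except earlier clinical failures. Earlier failures with no Visit 4 stay in, and those who do attend remain bound by the window. Add an entry to Section 5 that states this rule and how it relates to Protocol 10.1.4 and to the synopsis, which gives no exemption.

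Two tidying items in the same place carry no weight in the conclusion above. The compliance bullet cites a Section 3.3.7 that does not exist (compliance is in 3.3.6). The 80-100% range in SAP 3.2.4 and the protocol also differs from the 80-120% definition of compliant in SAP 3.3.6. The two should be reconciled, and any departure from the protocol listed in Section 5.

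The cost is one reworded bullet, one corrected cross-reference, the reconciled compliance range and short Section 5 entries, with no new data and no change to the primary analysis.

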### **3.3 Subject Data and Study Conduct**

#### *3.3.1 Subject Disposition*

Counts and percentages of subjects screened and in each of the analysis populations will be summarized by treatment and in total based on all screened subjects. Reasons for exclusion from each analysis population will also be summarized. Patients who were excluded from each of the study populations defined in Section 3.2, and their reasons for exclusion, will be listed.

Patient disposition by country and by site will also be summarized.

The counts and percentages of subjects completed, and who terminated early, along with the primary reason and secondary reasons for the termination (per study eCRF specifications) will be presented on CITT and MITT population.

#### *3.3.2 Protocol Deviations*

Protocol deviations are defined as violations from the procedures outlined in the protocol. Major protocol deviations are protocol violations likely to affect the study results and leading to the exclusion of the subject from the MPP.

Once the database has been completed and considered as “clean”, a data blind review will be conducted before the database lock in order to identify all major protocol violations and assign subjects into each of the analysis sets as defined in Section 3.2.

Patients with protocol deviations will be presented in the data listings. Counts and percentages of subjects with protocol deviations by deviation category will be summarized by treatment and in total based on CITT population.

The protocol deviations are considered critical (or very serious) and major (or serious), according to the following definitions:

- Critical or very serious: Deviations affecting / they have adversely affected the rights, safety or welfare of subjects and / or the quality and integrity of data
- Major or serious: Deviations that may affect / have adversely affected the rights, safety or welfare of subjects and / or the quality and integrity of data.

In addition, the protocol deviations related to COVID-19 will be categorized and summarized by treatment and in total based on CITT population separately.

### 3.3.3 Demographic and Baseline Characteristics

The following demographic and baseline characteristics will be summarized:

- Age (years) and age categories (<65 years, ≥65 years)
- Sex
- Childbearing potential
- Race
- Ethnicity
- Risk factors for otomycosis (exposure to excess moisture, trauma, use of hearing aids, topical otic antibacterial, quantitative or qualitative changes in earwax, other)
- Bilateral otomycosis (yes, no)
- Evaluable ear (left, right)
- Baseline pathogen (yes [fungal only, fungal and bacterial, bacterial only], no)
- Ear wick placement
- Baseline pathogen species

Demographic and baseline characteristics will be summarized with descriptive statistics or counts and percentages of subjects as appropriate by treatment and in total based on Safety, CITT, and MITT Population.

### 3.3.4 Medical History

Counts and percentages of subjects with medical history will be summarized by event/diagnosis/procedure by treatment and in total on CITT population.

### 3.3.5 Concomitant Medications

Concomitant medications (including rescue medication) taken during the course of the study or within 30 days prior to Screening are recorded. This also includes prescribed medications, over-the-counter medications and herbal supplements.

Concomitant medications will be coded to anatomical therapeutic chemical (ATC) class and preferred term using the World Health Organization Drug Dictionary Global (WHODrug Global B3, Sept 2019). For summary purposes, medications will be considered prior medications if they stopped prior to the first dose of study drug and concomitant medications if they were taken at any time after the first dose of study drug (i.e. started prior to the first dose of study drug and were ongoing or started after the first dose of study drug).

If a medication has incomplete start or stop dates, dates will be imputed to determine whether a medication should be considered prior or concomitant. If a medication start date is incomplete, the first day of the month will be imputed for missing day and January will be imputed for missing month. If a medication stop date is incomplete, the last day of the month will be imputed for missing day and December will be imputed for missing month. Incomplete start and stop dates will be listed as collected without imputation.

Counts and percentages of subjects taking prior and concomitant medications by ATC class and preferred term will be summarized by treatment and in total based on the CITT population.

The number of patients taking prohibited medications (as defined in the protocol section 6.7.1) will be tabulated by treatment group. A listing will also be provided.

The number of patients taking rescue medications (as defined in the protocol section 6.7.2) will be tabulated by treatment group. A listing will also be provided.

### 3.3.6 Study Drug Exposure and Compliance

Days of exposure to study drug will be calculated as (date/time of last dose of study drug – date/time of first dose of study drug) / 3600 / 24 + 0.5, rounded to the nearest half day. If time of last dose of study drug or time of first dose of study drug is missing, then days of exposure to study drug will be calculated as (date of last dose of study drug – date of first dose of study drug + 1).

Days of exposure to study drug will be summarized by treatment based on the CITT population with descriptive statistics and with counts and percentages of subjects with exposure in the following categories:

- <1 week (<7 days)
- 1 to <2 weeks (7 - <14 days)
- $\geq 2$  weeks ( $\geq 14$  days)

Study medication compliance will be assessed during the first 7 day of the treatment period, during the treatment period (first 14 days), and during the overall study.

Percent compliance to the study drug regimen will be calculated as  $100 \times$  number of vials actually administered / number of vials expected to be taken. The number of doses administered, the number of used vials returned for evaluable ear, and the number of unused vials returned for evaluable ear are all considered to determine the number of vials actually administered for 14-day treatment period and the overall study. The number of expected doses taken is the number of doses the patient was expected to take during that period. It is calculated based on the patient's duration of participation in the study. If a patient completes treatment, 14 doses are expected in the first 7 days of treatment. For treatment period, 28 doses are expected. If a subject does not complete treatment in the treatment period (first 14 days), then the expected number of doses for the overall study will be twice the number of days that the patient took study medication. If a patient discontinues early, the expected number of doses is based on the time of early discontinuation. Percent compliance to the study drug regimen will be summarized by treatment and age group (<65 years,  $\geq 65$  years) based on the Safety, CITT, MITT populations with descriptive statistics and with counts and percentages of subjects with compliance in the following categories:

- <80%
- 80-120%
- $>120$ %

Compliance will be listed for each patient. Patients will be considered “compliant” if their percent compliance is between 80% and 120%. The proportion of patients who were compliant and non-compliant during the treatment period and during the first 7 and 14 days of the treatment period will be tabulated by treatment group.

